To date, no studies have explored treatment options for non-daily smokers and, as a result, treatment guidelines are not available to guide patients or healthcare providers. The study will compare two treatments -- smoking cessation counseling alone versus counseling in combination with patients' choice of nicotine patch, gum, or lozenge -- on their effects on quitting smoking and reducing exposure to nicotine and cancer causing agents. Findings will identify which patients are most likely to benefit from each form of treatment (counseling, nicotine gum, patch, or lozenge) and will allow patients and providers to estimate their chances of success based on personal characteristics – for example, age, gender, level of smoking – and the treatment they chose. This study will determine if NRT is safe and effective for AA non-daily smokers. The program will be the first to examine treatment options for non-daily smokers and could directly contribute to the first evidence-based guidelines for treating the 9.7 million U.S. adult non-daily smokers for whom no guidelines currently exist.

[figure not shown]
II. RESEARCH PLAN AND DESIGN

A. Study Objectives

The objective of this study is to examine if NRT is an effective treatment option for AA non-daily smokers. Outcomes will be measured at weeks 12 and 26 and will include biologically confirmed smoking abstinence, nicotine intake, carcinogen exposure, days abstinent, NRT adherence and side effects.

B. Study Type and Design:

The proposed study is a randomized trial of 384 AA non-daily smokers randomized to receive either 5 sessions of smoking

Projected sample size by group using 2:1 randomization, whereby 67% are randomized to C+NRT and 33% are randomized to C

cessation counseling in combination with 12 weeks of nicotine patch, gum, or lozenge (C+NRT) or 5 sessions of smoking cessation counseling alone (C). We will use 2:1 randomization; for every patient randomized to C, two will be randomized to C+NRT (see Figure). The primary outcome is biologically-confirmed 7-day abstinence from smoking at 12 weeks. Patient- and provider-driven secondary outcomes include reductions in nicotine intake and carcinogen exposure, days abstinent, NRT adherence and side effects. Participants will be recruited from the University of Kansas Medical Center (KUMC) and Swope Health Central, a community-based primary care clinic in urban Kansas City that serves a predominately AA clientele.

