Specific Aim 2: To compare patient- and provider-desired outcomes -- e.g., nicotine intake, carcinogen exposure, number of days abstinent, and side effects – among AA non-daily smokers receiving C versus C+NRT and, within the C+NRT group, examine the choice of NRT and use during the treatment period. Hypothesis: Participants randomized to C+NRT will demonstrate significantly greater reductions in nicotine intake and carcinogen exposure and significantly more days abstinent, while experiencing no differences in side effects as participants randomized to C. Analytic strategy: We will utilize linear mixed models to longitudinally (week 12 and 26) compare nicotine and carcinogen exposure between the two groups, then subsequently examine the effects of the covariates listed in the measurement table above using a best subsets selection method for both nicotine and carcinogen exposure independently. A generalized linear mixed model approach will be used to model days abstinent, controlling for number of days in study, to assess the effect of treatment on this endpoint and best subsets selection will be used to examine the effects of covariates on this endpoint. For each of these models, based upon the sample size, we anticipate that ten to twelve covariates could be included in a final model. We will compare the prevalence of any side effect as well as each specific side effect, from baseline to week 12, between the two groups using the chi-square test. If there is a global difference we will examine, within the NRT group, if type of NRT impacts the side effect profile. Within the NRT group we will descriptively summarize the number and percent of subjects who choose each type of NRT. Subsequently we will describe and descriptively compare the percent of subjects within each of these subgroups who use the NRT of choice during the treatment period (i.e., percent of patients within the patch, gum, and lozenge groups who used the medication).

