
These doses represent a starting point. To enhance the ability of our findings to be translated into practice, counselors will educate participants about the relationship between cpd and NRT dosing and empower them to tailor use to be consistent with their smoking patterns, intensity of withdrawal and craving, and level of side effects. Participants will be taught that, if the NRT dose is adequate, they may still have urges during the day, but most of the time they will not feel strong physical cravings or discomfort. They will also be educated about side effects that may indicate a nicotine overdose (nausea, vomiting, cramps, dizziness) and the need for a dose reduction (i.e., fewer pieces of gum/lozenge per day, reduction from 24 to 16 or 12 hours per day that the patch is worn), as well as symptoms of withdrawal (e.g., irritability, restlessness, anxiety) and strong physical craving that may indicate the need for a dose increase (i.e., more pieces of gum/lozenge per day, increase to longer wear or a higher dose patch). Counselors will probe for smoking level, use of NRT (days used, amount used per day), side effects, symptoms of withdrawal and craving, and general experiences with the

medication during the week 1, 4, 6, 8, and 10 sessions and will provide guidance, as necessary, to ensure that the medication is working optimally for each participant. The PI and study physician will provide oversight on questions and issues that arise related to side effects, dose reductions and/or increases.

Overview of Major Study Events

		Enroll./ Baseline					EOT	Final Follow- Up
		Wk 0*	Wk 1	Wk 4	Wk 8	Wk 10	Wk 12*	Wk 26*
Screening/ Assessments	X	X		X	X		X	X
Intervention								
Counseling		X	X	X	X	X		
Medication Dispensing (C+NRT only)		X (3 to 9- day trial period)	X	X	X		X	

*in person; all other visits are by telephone; EOT=end of treatment

Procedures and Methods

An overview of major study events is provided in the adjoining table.

Initial Screening.

The initial screen will review inclusion/exclusion criteria. Those eligible will be scheduled to complete final eligibility screening within 14 days. All ineligible smokers will be referred to local resources.

Final Screening and Enrollment (Wk 0). Final eligibility screening will be conducted in person and will consist of a pregnancy test on women of childbearing age and obtaining informed consent.

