Side effects. Participants will be asked about symptoms commonly associated with quitting smoking and/or NRT (i.e., difficulty concentrating, irritability, skin rash, mouth/throat irritation, nausea, sleep disturbance, heart burn) Time Points: Wks 4,8,12
Covariates (Aims 1, 2 & 3)
Demographics. Includes gender, age, income, education level, marital status, and use of alcohol Time Point: Wk 0
Smoking history. Includes type of cigarette (menthol, non-menthol), days smoked per month, number of cigarettes smoked per day on days smoked, length of time smoking at current non-daily rate, age of smoking initiation, time to first cigarette of the day (nicotine dependence), use of cigarettes only or cigarettes in combination with alternative forms of tobacco (ATP; e.g., cigars, cigarillos), presence of other smokers in the home, and home smoking restrictions Time Point: Wk 0
Treatment. Includes treatment assignment (C, C+NRT) and, for those randomized to C+NRT, their choice of nicotine gum, lozenge, or patch.

Clearly indicate which procedures, tests, visits, etc., are parts of usual standard therapy and which are performed solely for research purposes.

All tests, procedures, and visits are being performed solely for research purposes and are not billable to insurance companies.

Describe the fate of any body component (blood, CSF, bone marrow, etc.) used in the study, emphasizing confidentiality of labeling of the sample and the sample's destruction or storage.

Samples will be labeled only with a unique study identification number and only members of [name] and [name]'s team will have access to the samples. Samples will be disposed of one month after the final report is sent out to the Principal Investigator, unless participants agree to have their urine stored for future testing.

F. Risk/benefit assessment:

Physical risk

Risks for participating in the study are primarily those related to the use of NRT for participants randomized to the C+NRT arm. The safety of NRT has been demonstrated in hundreds of studies spanning over 30 years of research, including studies of patients who are very low level smokers and nonsmokers. To minimize any possible risk, we will exclude any patients with unstable heart disease (i.e., unstable angina or AMI in the past 4 weeks) per the medical contraindications for NRT.

Nevertheless, NRT, particularly in continuing smokers, can be associated with nausea, jitteriness,

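### The any-side-effect comparison pools withdrawal-type symptoms with NRT product effects, so a null result is weak support for no difference in side effects, and the list shows no item for four NRT harms the protocol names

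*Combined protocol and SAP*

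**What the plan says.** The side-effects row of the measures table in Section II.E states: "Participants will be asked about symptoms commonly associated with quitting smoking and/or NRT (i.e., difficulty concentrating, irritability, skin rash, mouth/throat irritation". The other three items on the list are heartburn, sleep disturbance and nausea. The questions are put at Weeks 4, 8 and 12.

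The Aim 2 analytic strategy in Section II.C plans chi-square tests on these items: "We will compare the prevalence of any side effect as well as each specific side effect, from baseline to week 12, between the two groups". The hypothesis is that the arms do not differ in side effects; no margin is given. The same paragraph looks at NRT type within the C+NRT arm if there is a global difference, a term it does not define.

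Elsewhere the protocol separates the two kinds of symptom. The NRT dosing text in Section II.E speaks of "side effects that may indicate a nicotine overdose (nausea, vomiting, cramps, dizziness" on one side and "symptoms of withdrawal (e.g., irritability, restlessness, anxiety" on the other. It treats the first as pointing to too much nicotine and the second to too little. The risk section (II.F) says that "NRT, particularly in continuing smokers, can be associated with nausea, jitteriness"; it also lists vivid dreams and insomnia.

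The Rationale (I.C) sets the aim: "This study will determine if NRT is safe and effective for AA non-daily smokers".

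**The concern.** One list holds symptoms that the protocol itself reads as opposite signals. Irritability is on it as a withdrawal sign; nausea is on it as a possible sign of excess. Rash, mouth/throat irritation and heartburn are product effects. Difficulty concentrating is probably withdrawal-type, but that is inference. Sleep disturbance could be either.

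A composite that counts a participant once for any of these has two weaknesses. A participant already counted for irritability cannot be counted again for a product effect, so a real difference in product effects is diluted. If NRT also relieves withdrawal, the two differences pull in opposite directions. In both cases the result moves toward equality, which is the hypothesis, so a null composite says little about tolerability.

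This matters because the Background (I.B) records the worry that NRT might deliver more nicotine than non-daily smoking does, and participants are taught to tailor their own use. Harm from excess nicotine is therefore a central safety question, yet several signs of it that the protocol names have no visible place on the list.

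**Working it through.** **1. Reproducing the plan's power.** The only power figures in the plan are for Week 12 abstinence with 128 in C and 256 in C+NRT. I used the two-sided 5% chi-square approximation with pooled variance under the null and no continuity correction:

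power = Φ[(d − 1.96·SE0)/SE1] + the negligible opposite tail, where d is the difference, SE0 = √[p̄(1−p̄)(1/128 + 1/256)], SE1 = √[p1(1−p1)/128 + p2(1−p2)/256], and p̄ = (128·p1 + 256·p2)/384.

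| C vs C+NRT | Plan | Recomputed |
|---|---|---|
| 10% vs 25% | 95% | 95.7% |
| 10% vs 22.5% | 87% | 87.6% |
| 10% vs 20% | 71% | 71.7% |

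The plan's figures reproduce, so the same formula is used below.

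**2. Model for the composite.** Let W be any withdrawal-type symptom and H any product effect. Assuming independence, P(any) = 1 − (1−W)(1−H). The documents give no symptom rates; every W and H here is an assumption.

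**3. Dilution without cancellation.** H is 15% in C and 35% in C+NRT; W is 50% in both.

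- C: 1 − 0.50 × 0.85 = 57.5%. C+NRT: 1 − 0.50 × 0.65 = 67.5%. A 20-point difference shows as 10 points.
- Composite: p̄ = 0.6417, SE0 = 0.0519, SE1 = 0.0526; (0.10 − 1.96 × 0.0519)/0.0526 = −0.03; power about 49%.
- Product effects alone: p̄ = 0.2833, SE0 = 0.0488, SE1 = 0.0434; (0.20 − 1.96 × 0.0488)/0.0434 = 2.40; power about 99%.

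**4. Range over the assumptions.** H stays at 15% vs 35%, so power for product effects alone is 99% in every row.

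| W in C vs C+NRT | Any: C vs C+NRT | Composite power |
|---|---|---|
| 30% vs 30% | 40.5% vs 54.5% | 74% |
| 50% vs 50% | 57.5% vs 67.5% | 49% |
| 70% vs 70% | 74.5% vs 80.5% | 28% |
| 50% vs 45% | 57.5% vs 64.25% | 25% |
| 50% vs 40% | 57.5% vs 61.0% | 10% |
| 50% vs 35% | 57.5% vs 57.75% | 5% |
| 50% vs 55% | 57.5% vs 70.75% | 73% |

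The 50% vs 35% row is close to exact cancellation: 1 − 0.65 × 0.65 = 57.75% against 57.5%. The last row lets withdrawal be worse with NRT; the composite is still less powerful than product effects alone.

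**5. Listed and named harms.**

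| Source | Named | No item on the list |
|---|---|---|
| NRT dosing text (II.E), overdose signs | nausea, vomiting, cramps, dizziness | vomiting, cramps, dizziness (3 of 4) |
| Risk section (II.F) | nausea, jitteriness, insomnia, vivid dreams | jitteriness; vivid dreams too, if sleep disturbance does not cover them (1 to 2 of 4) |

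Adverse events are tracked at scheduled visits and by spontaneous report, according to the safety text just before Section III. The available text shows no between-arm comparison of them. Part of that safety text was removed from the documents reviewed, so this absence is not certain.

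**The case against.** The strongest reply is that the sentence defining the composite also promises a test of each specific side effect. That stands: an excess of nausea or rash, or a deficit of irritability, remains visible item by item. A reader might infer that the plan hides product harms altogether; it does not. What the item tests leave untouched is the composite itself, any conclusion drawn from a null composite, and symptoms that are not asked about.

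Second, the global difference that triggers the NRT-type look is not defined as the composite; the preceding sentence names both the composite and the item tests. This also stands. The gate is affected only if the term means the composite.

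Third, cancellation depends on chosen rates, and its direction is not established. The plan expects only 10% abstinent in C and 20–25% in C+NRT at Week 12. More quitters in C+NRT could mean more withdrawal there. It would therefore be wrong to infer that the composite is bound to come out equal. Dilution, however, does not need withdrawal to differ between arms.

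Fourth, a reader might say that the list omits most of the harms the protocol names. That depends on the count. It is 4 to 5 of 7 across the dosing and risk sections, 1 to 2 of 4 in the risk section alone, and 4 to 5 of 10 if the list's own product effects (rash, mouth/throat irritation, heartburn) are counted. The full instrument is not in the documents, and the table row may be a summary. The supportable statement is that four named symptoms show no item.

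Finally, overall symptom burden is a legitimate outcome for patients and providers, and Section II.F aims to keep the number of items small. Both are fair. Neither makes the mixed composite a good test of whether NRT is tolerated.

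**Conclusion.** The point holds in a limited form, with moderate confidence, as an inexpensive improvement. The any-side-effect composite mixes symptoms that the protocol reads in opposite ways, so a null result on it is weak support for the no-difference hypothesis.

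The size cannot be known from the documents. Under the assumed product-effect rates of 15% and 35%, with independence and withdrawal equal in the two arms at 30% to 70%, composite power is 74% down to 28%, against 99% for product effects alone. It falls to about 5% if withdrawal drops from 50% to 35% under NRT. Cancellation is possible, not demonstrated.

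Separately, vomiting, cramps, dizziness and jitteriness have no item on the list as shown. They may be caught as adverse events, but no comparison of those between arms is visible in the available text.

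**What to change.** In the Aim 2 analysis (Section II.C):

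- Prespecify any product effect as the tolerability comparison: skin rash, mouth/throat irritation, nausea, heartburn and the added items below.
- Report any withdrawal symptom (irritability, difficulty concentrating) as a separate summary.
- Report sleep disturbance on its own.
- Keep the item-level tests.
- Define the trigger for the NRT-type look as the product-effect summary, or make that look descriptive whatever the result.

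In the side-effects row of the measures table (Section II.E), add yes/no items for vomiting, cramps, dizziness and jitteriness at Weeks 4, 8 and 12.

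The cost is four short questions at three contacts, against the stated wish to limit items, and a change of analysis wording. There would be two summaries instead of one. Some symptoms will not fall cleanly into either group, so the assignment should be fixed before the data are compared by arm.

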Counseling Visits (Wks 0,1,4,8,10). Counseling sessions will be completed by phone at Wks 1,4, 8,10, and in person at Wk 0. The number of sessions is consistent with our previous studies where we have achieved visit completion rates of around 80%.^{45,55,56}

NRT Dispensing (Wks 0-1). Participants randomized to C+NRT will be given a trial supply of nicotine gum, patch, and lozenge and be instructed to try each for 3-days. After the 3 to 9-day trial period, they will select and be mailed a 4 week supply of the medication of their choice. They will receive refills of their selected medication at the Weeks 4 and 8 study visits.

Biological Sample Collection (Wk 0,12,26). Urine will be collected three times throughout the study for biochemical verification of cessation at Wk 12 and Wk 26, nicotine intake at Wks 0, 12, 26, and carcinogen exposure at Wks 0, 12, and 26. Additional details regarding each assay are provided in the Measures and Assessment Time Points table.

Retention. We have developed a system of reminders and compensation that have resulted in impressive retention rates in our previous clinical trials. Reminders. One week prior to each scheduled visit a reminder postcard noting the scheduled appointment date and time will be mailed to participants. In addition, participants will be called up to 6 times to remind them of their upcoming visit. A detailed tracking database, with an automated reminder system, will notify counselors of when to send postcards and complete reminder phone calls. Compensation. Participants will be given a \$40 electronically loaded gift card at Wks 0, 12 and a \$20 electronically loaded gift card at Wks 1, 4, 8, 10, 26 in appreciation for their time and participation.

Measures

Our selection of measures (see table) and the measurement time points have been driven by our patient and stakeholder advisory panels.

Measure and Assessment Time Points

Primary Scientific Outcome (Aim 1)

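### The two-arm side-effect checklist has no Week 0 or Week 1 value, so the Aim 2 comparison cannot isolate new symptoms and loses power

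*Combined protocol and SAP*

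**What the plan says.** Section II.C, Specific Aim 2, sets out the analysis: "We will compare the prevalence of any side effect as well as each specific side effect, from baseline to week 12", by chi-square between the two arms. The hypothesis is that C+NRT participants will do better on exposure and days abstinent "while experiencing no differences in side effects as participants randomized to C". If a global difference appears, the plan goes on to ask whether the type of NRT affects the side-effect profile.

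The Measures table in II.E defines the outcome. "Participants will be asked about symptoms commonly associated with quitting smoking and/or NRT"; the list and schedule read "difficulty concentrating, irritability, skin rash, mouth/throat irritation, nausea, sleep disturbance, heart burn) Time Points: Wks 4,8,12". No recall window is given.

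Other parts of II.E bear on early exposure:

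- **NRT Dispensing (Wks 0-1).** C+NRT participants receive gum, patch and lozenge to sample and will "be instructed to try each for 3-days". They choose one product once this sampling, which may last from 3 to 9 days, is over.
- **NRT dosing.** "Counselors will probe for smoking level, use of NRT (days used, amount used per day), side effects, symptoms of withdrawal and craving", and Week 1 is among the sessions listed.
- **Counseling and Written Materials.** Counseling is the same in both arms, except that medication use is raised only with the NRT group.

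The adverse-event text at the end of section II adds tracking at scheduled visits and by spontaneous report.

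**The concern.** The analysis window and the measurement schedule do not match. The window opens at baseline, but the instrument used in both arms is first applied at Week 4. Two things are lost.

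First, there is no pre-treatment symptom value. Irritability, poor concentration, disturbed sleep, nausea and heartburn can all be present before anyone receives NRT, and the plan itself links the list to quitting as well as to NRT. Without a Week 0 record, onset after randomization cannot be derived for any participant.

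Second, C+NRT participants may sample up to three products in the first 3 to 9 days, and no matched two-arm measure sits close to that period.

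Background symptoms shrink the difference between arms, and a small, non-significant difference is what Aim 2 predicts. Section I.C also says that the study will settle whether NRT is safe in this population. The by-product analysis is conditional on a global difference, so a diluted overall test could also prevent that analysis.

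**Working it through.** **1. Schedules side by side.** Nicotine intake and carcinogen exposure are measured at Wks 0, 12 and 26. Days abstinent is recorded at Wks 1, 4, 8, 10 and 12. Side effects are recorded at Wks 4, 8 and 12. Of these between-arm Aim 2 outcomes, only side effects have neither a Week 0 nor a Week 1 value. Week 4 is about day 28 and the product trial ends by day 9 if it starts at Week 0, so the first checklist comes at least 28 − 9 = 19 days after the trial.

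**2. The plan's own power figures.** The documents give no power for side effects, so I checked the method on the abstinence figures in II.C (128 C, 256 C+NRT, chi-square, 5% type 1 error). The pooled two-sided approximation is

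power = Φ{ [ |p2 − p1| − 1.96·√(p̄(1 − p̄)(1/n1 + 1/n2)) ] / √(p1(1 − p1)/n1 + p2(1 − p2)/n2) }.

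It gives 95.7%, 87.6% and 71.7% for 10% against 25%, 22.5% and 20%. The plan states 95%, 87% and 71%, so its figures reproduce. Exact enumeration of the same uncorrected test gives 96.0%, 88.3% and 72.9%; I use exact enumeration below.

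**3. Illustration of dilution.** Every symptom rate here is an assumption.

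- New symptoms without NRT: e1 = 10%.
- NRT produces a new symptom in 15% of those who would otherwise have none: e2 = 1 − 0.90 × 0.85 = 23.5%.
- Pre-existing prevalence b: equal in both arms, independent of new onset, and still reported after baseline.
- Every participant answers the checklist.

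Without a Week 0 value, the observed rate in each arm is b + (1 − b)e. At b = 50%:

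- C: 0.50 + 0.50 × 0.10 = 55%.
- C+NRT: 0.50 + 0.50 × 0.235 = 61.75%.

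With a Week 0 value, the analysis can be restricted to those symptom-free at entry. The comparison is then 10% against 23.5% in 128(1 − b) and 256(1 − b) participants.

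| Pre-existing b | Any symptom, C vs C+NRT | Power, no Week 0 value | Symptom-free n | Power, new onset |
|---|---|---|---|---|
| 30% | 37% vs 46.5% | 43% | 90 / 179 | 79% |
| 50% | 55% vs 61.8% | 25% | 64 / 128 | 65% |
| 70% | 73% vs 77.1% | 15% | 38 / 77 | 42% |

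**4. A smaller effect.** With new-onset rates of 10% against 20% and b = 20%, the observed rates are 28% and 36%. Power by the approximation in step 2 is 34%, against 61% for new onset in the symptom-free.

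**5. Single symptoms.** Applying the same 15% NRT effect to one symptom, with background rates of 5%, 10% and 20%, gives C+NRT rates of 19.25%, 23.5% and 32%. Power is 99%, 92% and 71%. Dilution is therefore mainly a problem for the composite, and for individual symptoms that are common without NRT.

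**The case against.** The case on the other side is substantial, and most of it limits the point rather than removing it.

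**The window may mean the treatment period.** Prevalence over an interval, compared between arms, need not mean change from baseline, and no baseline score is expressly promised. That stands. Even so, the checklist does not visibly cover Weeks 0 to 4 unless the Week 4 question reaches back, which the plan does not say.

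**Early side effects are asked about.** A reader might infer that nothing is asked when exposure starts. The documents do not support that: counselors probe at Week 1, and adverse events are tracked at visits and by spontaneous report. What is missing is narrower. Neither source is named as Aim 2 data. The probe serves medication management, and medication use is discussed only in the NRT arm, so it may yield no comparable C value. Some text before the adverse-event paragraph was not available to me, so I make no judgment on safety collection as a whole.

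**Randomization protects the comparison.** A reader might infer bias between arms. Pre-existing symptoms are balanced in expectation and type I error is not inflated. The loss is in power and interpretability.

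**Each symptom is already compared separately.** This stands. Product-type complaints such as rash or mouth irritation will be visible on their own, and step 5 shows good power where background is low.

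**The composite need not saturate.** A reader might multiply seven symptoms by three visits and, at 10% each, reach 1 − 0.9^21 = 89%. That treats 21 reports as independent. If a symptom fully persists across visits, the figure is 1 − 0.9^7 = 52%. The documents support neither rate.

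**Participant burden.** Patient and stakeholder panels drove the measures and time points, and the plan undertakes to limit items. That weighs against long additions, but hardly against seven short questions.

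**Conclusion.** The point holds as a measurement gap in a secondary outcome. The two-arm checklist has no pre-treatment value and no Week 1 value, so treatment-emergent symptoms cannot be derived. The consequence is dilution, mainly of the any-side-effect comparison, in a test whose hypothesis is no difference. That comparison also appears to gate the by-product analysis, although the plan does not define a global difference.

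Under the assumed rates, power falls to 25% where a Week 0 value would allow 65%, with 50% pre-existing. The pairs are 43% and 79% at 30%, and 15% and 42% at 70%. The direction holds across this range and for the smaller effect in step 4. The size depends on rates that the documents do not give.

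A reader might also infer a recovery to 92% by testing 10% against 23.5% in all 384 participants. That assumes people who already have symptoms develop further new ones at the same rates, so I do not rely on it. No figure stated in the plan is wrong. This is an inexpensive improvement and does not affect the primary outcome.

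**What to change.** 1. Add the same seven-item checklist to the Week 0 survey, before any NRT is given, and to the Week 1 call, in both arms and with identical wording.
2. State the recall window at each contact. Asking about the time since the previous checklist would cover the product trial even when it runs past the Week 1 call.
3. In II.C, Specific Aim 2, define the comparison as treatment-emergent symptoms (absent or milder at Week 0). Keep the planned comparison of each symptom, and say which result counts as the global difference.
4. For participants already enrolled without a Week 0 checklist, pre-treatment status cannot be recovered. Reword the Aim 2 window for them to match what was measured at Weeks 4, 8 and 12.

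The cost is about a minute of questions at each of two contacts that already take place in both arms, plus the analysis wording. No extra visits or staff are needed.
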